1 BACKGROUND AND RATIONALE

Worldwide, the prevalence of cerebral palsy (CP) is 1.77-2.9 per 1000 live births.^{i,ii,iii} CP describes a group of developmental disorders of movement and posture, attributed by a non-progressive interference, lesion, or abnormality in the immature brain, causing activity restriction or disability. CP is a complex condition that is also accompanied by disturbance in sensation, cognition, communication and/or behaviour as well as secondary musculoskeletal problems.^{iv} Common musculoskeletal problems in CP include spasticity and weakness which affect gait.

Among the treatment modalities for CP, transcutaneous electrical nerve stimulation (TENS) or neuromuscular electrical stimulation (NMES) is one intervention that has been shown to be effective in muscle tone reduction. A systematic review showed significant evidence, based on 14 randomised controlled trials (RCTs) with 550 study participants evaluating the effect of TENS, for management of limb spasticity.^v Another review of electrical stimulation for children with CP showed that use of NMES offered benefits such as increased muscle strength, range of motion and function in children with CP.^{vi} In combination with dynamic splinting, NMES was more effective than either treatment on its own in improving function and posture. Two out of six TENS studies in a systematic review evaluating efficacy of electrical stimulation in improving motor function of children in CP reported statistically significant improvements, two studies reported no statistically significant effects but documented a perceived positive treatment effect as reported by parents/carers, and the remaining two case reports described improvements.^{vii} A randomised placebo-controlled trial was conducted to investigate the efficacy of NMES and TES in 60 children with cerebral palsy.^{viii} The electrical stimulation was only tested in legs with two electrodes (one proximal and one distal position). After 16 weeks of treatment, no differences were observed for strength or function. However, statistically significant differences were observed between NMES and TES versus placebo for impact of disability, and the difference continued at the 6 week follow-up between TES versus placebo.

1.1 General Introduction

The Mollii suit is a new technology of electrical stimulation in the form of whole-body garment with multiple electrodes individually programmed to stimulate the selected muscles. Based on preliminary studies, it is suggested that the Mollii suit improves spasticity. Recent studies also proposed that it improves mobility, gait, function and quality of life. However, these studies are based on qualitative and subjective measures.

1.2 Rationale and Justification for the Study

Living with CP is challenging for the child as well as the family charged with their care and support needs. Many families seek effective and sustainable interventions to improve gait of their children with CP. Many families, however, are unable to adhere to frequent intensive centre-based therapy in view of its high cost and time commitment. An intervention that could be used at home, assessed periodically by health care professionals of a tertiary pediatric centre, that has a benefit on gait and motor function in children with CP might be feasible to families in the local Singapore healthcare setting.

1.2.1 Rationale for the Study Purpose

Considering the potential of the Mollii Suit and the need for evidence, we aim to study the effectiveness in improving gait and the feasibility with the use of the Mollii suit in children with cerebral palsy in Singapore.

1.2.2 Rationale for Doses Selected

Preliminary studies have shown that the Mollii suit is effective with one hour every day to every other day use for as 2-8 weeks. After discussion with the industrial partner and with the primary objective of a change in gait in mind, a dosage of 1 hour every day for 4 weeks was decided.

1.2.3 Rationale for Study Population

Studies have shown that the Mollii suit was effective in improving spasticity and reducing pain in adults post stroke and children with cerebral palsy.^{ix,x,xi,xii,xiii} As we are studying improvement in gait, ambulant children with cerebral palsy is the target population and they have spasticity as their dominant motor feature.

1.2.4 Rationale for Study Design

This is a single-centre study that compares subjects before and after the intervention. As a wide range of age group is used in the study population, comparison is made in gait in the same individual.

2 HYPOTHESIS AND OBJECTIVES

2.1 Hypothesis

The Mollii suit is effective in improving gait in ambulant children with cerebral palsy

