2.2 Primary Objectives

The primary objective is to assess the effectiveness of the Molli suit in improving gait in children with cerebral palsy, GMFCS I-III.

Change in Gait Profile Score will be computed as primary outcome measure. Other measurements obtained in the gait analysis include Gait deviation index, gait speed and cadence etc.

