4 STUDY DESIGN

This study will evaluate the effectiveness of improving gait with the use of the Mollii suit in children

with cerebral palsy with instrumented 3-dimensional gait analysis and objective standardised assessment tool at pre-intervention and at 1 month post intervention.

This study will evaluate change in gait and function following a four week intervention period using a protocol of wearing the Mollii suit for one hour every day for four weeks.

This study also evaluates the feasibility of the use of the Mollii suit intervention protocol by conducting qualitative interviews with parents immediately and 1 month after the intervention. Information on compliance, perception of acceptability, benefits or concerns, practicalities, cost and likelihood of using the intervention in the future will be collected.

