4.1 Randomisation and Blinding

Randomisation and blinding will not be performed.

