6.5 Blinding

Blinding is not done.

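### The hypothesis and primary objective ask whether the suit is effective, but an open-label single-group before-after comparison can only show whether gait changed

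*Protocol*

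**What the plan says.** Four places in the protocol frame the main question as the effect of the suit on gait:

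- Section 2.1 (Hypothesis): "The Mollii suit is effective in improving gait in ambulant children with cerebral palsy".
- Section 2.2 (Primary Objectives): "to assess the effectiveness of the Molli suit in improving gait in children with cerebral palsy".
- Section 1.2.1 (Rationale for the Study Purpose): "we aim to study the effectiveness in improving gait and the feasibility with the use of the Mollii suit".
- Section 4 (Study Design): "This study will evaluate the effectiveness of improving gait with the use of the Mollii suit".

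The design is stated openly. Section 1.2.4 describes a single-centre comparison of subjects before and after the intervention and gives one reason for it: because ages vary widely, "comparison is made in gait in the same individual". Section 4.1 states "Randomisation and blinding will not be performed", and section 6.5 states "Blinding is not done". Section 6.6 lets regular standard care continue. Section 9.1 bases the sample size on a two-sided paired t-test, and section 3.1 enrols up to 20 children.

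The text also contains a more modest question. Section 2.2 names the change in Gait Profile Score as the primary outcome, and section 4 says "This study will evaluate change in gait and function following a four week intervention period".

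**The concern.** To call the suit effective is to say that gait improved because of it. That requires knowing what would have happened over the same weeks without the suit, and this design has no source for that. The reason given in section 1.2.4 supports comparing a child with himself or herself rather than with children of other ages. It says nothing about change that would have occurred anyway.

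Several things other than the suit could move the mean score between the two gait analyses: familiarity with the gait laboratory, effort in a child and family who know the suit is on trial, other care that continues, and natural change in growing children. Instrumented gait analysis limits assessor subjectivity but controls none of these.

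At stake is the conclusion of the trial. Section 13 plans a peer-reviewed publication. With section 2.1 as the hypothesis and section 9.1 as the test, a significant result would naturally be reported as support for effectiveness, and no sentence in the protocol holds that reading back.

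**Working it through.** **Inputs.** Difference of interest 1.6 points of Gait Profile Score, SD 2.4, two-sided alpha 0.05 and power 80% (section 9.1); n = 20 (section 3.1). The SD is read as the SD of the pre-post change.

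**Step 1: reproduce the plan's figure.** The standardised difference is 1.6 / 2.4 = 0.667. With the noncentral t distribution, a two-sided paired t-test has power 78.5% at n = 19 and 80.7% at n = 20, so 20 is the smallest sample that reaches 80%. This agrees with section 3.1 and supports reading 2.4 as the SD of change. The sample size is therefore right for a one-group question.

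**Step 2: what the test tests.** Write the mean change as suit effect + drift, where drift is the mean change from everything other than the suit. The paired t-test has the null hypothesis that this sum is zero. With one group the two terms cannot be separated, whatever the sample size. The hypothesis in section 2.1 concerns the first term alone.

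**Step 3: how sensitive the result is to drift.** Set the suit effect to zero and let the drift d act in the direction of improvement.

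- Standard error of the mean change = 2.4 / √20 = 0.537.
- Critical t on 19 degrees of freedom = 2.093.
- Noncentrality = d / 0.537.
- P(significant improvement) = upper tail of the noncentral t beyond 2.093.

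| Assumed drift d | Noncentrality | P(significant improvement), suit effect zero |
|---|---|---|
| 0 | 0 | 2.5% |
| 0.4 | 0.75 | about 11% |
| 0.8 | 1.49 | 29% |
| 1.0 | 1.86 | 42% |

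The drifts of 0.4, 0.8 and 1.0 are 25%, 50% and 62.5% of the 1.6 points that the plan takes as clinically important. They are assumptions. The documents give no figure for drift, so the table shows sensitivity and is not an estimate of bias.

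**Step 4: is there a comparator elsewhere?** The 1-month visit in Table 1 of section 4.3 is again within-child and has no gait analysis. The control units in section 15 are equipment supplied with the suits and are not a control group. Neither provides a reference for change without the suit.

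**Step 5: what a controlled test would need, for scale only.** Assume two equal groups, a between-group difference in change of 1.6 and an SD of 2.4 in each. Then 80% power needs about 36 per group (normal approximation) or 37 (t), which is 72 to 74 children. Twenty children split 10 and 10 would have about 29% power (t) to 32% (normal). Keeping the design and matching the question to it is thus the practical route.

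**The case against.** The best reply is that this is a matter of wording. The before-after design is declared, nothing is hidden, and the protocol already says what it will measure: change in Gait Profile Score in section 2.2 and change after four weeks in section 4. Section 9.2 plans descriptive analysis and sets no success criterion. A caution about interpretation might also sit in a statistical analysis plan that is not shown.

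Much of this is true, and it limits the point without removing it. The sentences about change do not withdraw the causal hypothesis, so the protocol carries two questions and its design answers only one of them. A later analysis plan could add a caution, but the hypothesis and the design are both fixed in the protocol, and it could not make them fit each other.

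A reader might infer more than the documents support:

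- *That the single-group design is itself an error.* It is a declared choice and can estimate a before-after change and study feasibility.
- *That the protocol will declare a significant test to be proof.* No passage says so. The risk comes from setting section 2.1 beside section 9.1.
- *That drift of a known size is present.* None is given. Regression to the mean in particular is possible but not forced, because sections 3.3 and 3.4 set no threshold on Gait Profile Score.
- *That the significance threshold is too lenient.* An observed mean change of 2.093 × 0.537 = 1.12, or 70% of 1.6, would be significant. But any two-sided 5% test with 80% power has a threshold near 1.96 / 2.80 = 70% of its target, including in a randomised trial. This says nothing about the missing control.
- *That the baseline window is the problem.* Section 4.3.2 allows baseline up to two weeks before fitting, but an interval of exactly four weeks would leave attribution just as open.
- *That changes in care go unrecorded.* The diary and later questionnaires are in annexes that are not shown and may cover this.

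**Conclusion.** The point holds as a mismatch between question and design. Sections 2.1 and 2.2, repeated in 1.2.1 and 4, ask whether the suit works. The open-label, one-group paired comparison can say only whether the mean score changed while the suit was in use and other care continued, and no passage limits the causal reading.

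That conclusion follows from the design and needs no assumed number. The illustrative size, a chance of a significant improvement of about 11%, 29% or 42% instead of 2.5% with no suit effect, rests on drifts of 0.4, 0.8 or 1.0 points, 20 children completing both gait analyses, and 2.4 being the SD of change. The arithmetic of the sample size is sound and the data remain usable. The claim attached to them should be changed before results are known.

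**What to change.** 1. Reword sections 2.1 and 2.2, and the matching sentences in sections 1.2.1 and 4, along these lines: *to estimate the within-child change in Gait Profile Score from baseline to the end of four weeks of suit use*. The feasibility aim stays as it is.
2. Add one sentence, for example in section 9.2: *a statistically significant change will not by itself be attributed to the suit, because practice, effort, other care and natural change are uncontrolled*.

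This costs edits in four places and one added sentence, in a protocol amendment notified under section 12. Sample size, visits, outcome, test and permitted care do not change. The downside is a more modest claim. If the sponsor wishes to keep the effectiveness question, a concurrent control and a new sample size calculation would be needed.

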2.2 Primary Objectives

The primary objective is to assess the effectiveness of the Molli suit in improving gait in children with cerebral palsy, GMFCS I-III.

Change in Gait Profile Score will be computed as primary outcome measure. Other measurements obtained in the gait analysis include Gait deviation index, gait speed and cadence etc.

2.3 Secondary Objectives

The secondary objective is to evaluate the acceptability, tolerance and compliance of the Molli suit in children with cerebral palsy.

2.4 Potential Risks and Benefits:

2.4.1 Potential Risks

Mollii suit may cause discomfort or tingling sensation to some people. Some people may have allergic reaction to the material of the suit. Otherwise, there is minimal risk in wearing the suit if

there are no contraindication.

2.4.2 Potential Benefits

The Mollii suit is potentially an effective adjunct intervention for children with cerebral palsy that can benefit gait and motor function. It can potentially reduce number of visits needed to tertiary hospital as the intervention can be performed at home. It will also reduce reliance on hospital based care and improve convenience for families.

3 STUDY POPULATION

3.1 List The Number and Nature of Subjects to be enrolled

This is a single centre study that will enrol up to 20 children with cerebral palsy.

3.2 Criteria for Recruitment and Recruitment Process

The eligible participants will be recruited from the families who receive services and/or medical follow-up at KKH. Information of the study and Consent Form will be provided to the families who show interest in the study.

3.3 Inclusion Criteria

- Aged 4-18
- GMFCS level I to III
- Spasticity as the dominant motor feature
- Children agree to wear the Mollii suit as per procedures and consent to the study
- Parents/carers agree to assist their child to wear the Mollii suit as per procedures
- Medical practitioner's approval

3.4 Exclusion Criteria

- Individuals with electrical implanted stimulatory device
- Individuals with medical devices that are affected by magnets, such as programmable shunts.
- Individuals with cardiovascular diseases, infectious diseases, malignance (cancer), fever, pregnancy, rashes or skin problems.
- Individuals who have had Botulinum toxin done 6 months prior intervention or soft tissue release surgery done 6 months prior intervention.
- Individuals who have had change in oral medication for spasticity 1 month prior intervention.

3.5 Subject Replacement

Subjects who drop out will not be replaced.

4 STUDY DESIGN

This study will evaluate the effectiveness of improving gait with the use of the Mollii suit in children

with cerebral palsy with instrumented 3-dimensional gait analysis and objective standardised assessment tool at pre-intervention and at 1 month post intervention.

This study will evaluate change in gait and function following a four week intervention period using a protocol of wearing the Mollii suit for one hour every day for four weeks.

This study also evaluates the feasibility of the use of the Mollii suit intervention protocol by conducting qualitative interviews with parents immediately and 1 month after the intervention. Information on compliance, perception of acceptability, benefits or concerns, practicalities, cost and likelihood of using the intervention in the future will be collected.

4.1 Randomisation and Blinding

Randomisation and blinding will not be performed.

4.2 Contraception and Pregnancy Testing

Not applicable.

4.3 Study Visits and Procedures

Table 1: Assessment timeline and persons reporting or conducting the assessments.

	Parent	Child	Assessor	Measure
At Baseline				
Demographics, resource use questionnaire	X	X		Questionnaire
Instrumented 3D Gait analysis		X	X	Gait kinetics and kinematics
EQ-5D	X	X		QoL/ health status
ICF	X		X	Performance/Body structure & function
GMFM		X	X	Performance/ activity (ICF)
FAQ	X	X	X	Performance/Body structure & function
10m walk test		X	X	Performance/ activity (ICF)
GAS	X	X	X	Expectation
Daily during the 4 week intervention				
Study Diary- compliance; activity;	X			
Pain	X	X		
Immediately post intervention				
Instrumented 3D Gait analysis			X	Gait kinetics and kinematics
EQ-5D	X	X		QoL/ health status
ICF	X		X	Performance/Body structure & function
GMFM		X	X	Performance/ activity (ICF)
FAQ	X	X	X	Performance/Body

				structure & function
10m walk test		X	X	Performance/ activity (ICF)
GAS	X	X	X	Expectation
Feasibility/ Acceptability	X			Questionnaire
1 months post intervention				
EQ-5D	X	X		QoL/ health status
ICF	X		X	Performance/Body structure & function
GMFM		X	X	Performance/ activity (ICF)
FAQ	X	X	X	Performance/Body structure & function
10m walk test		X	X	Performance/ activity (ICF)
Feasibility/ Acceptability	X			Questionnaire

4.3.1 Screening Visits and Procedures

All KKH patients who are attending outpatient clinics for neurology service and/ or Physiotherapy and are diagnosed with cerebral will be screened accordingly to the inclusion and exclusion criteria as stated in the preceeding sections 3.2 to 3.4 by the doctors and/or physiotherapists in the clinic. Consent will be taken by anyone in the study team.

4.3.2 Study Visits and Procedures

Baseline

Prior to commencement of intervention (within 2 weeks prior to fitting of Mollii suit), the child will undergo:

I. An instrumented 3-dimensional gait analysis

For the 3-dimensional gait analysis, patient is required to walk on a walkway of approximately 8 to10 metres long with 2 force-plates along the walkway. The patient will have skin markers placed on their body, majority on the lower extremities following the Plug-in Model marker placement model by physiotherapist. The patient will be required to walk barefoot with and/or without walking aid repeatedly along the walk-way until 6 to 8 successfully clean strike on the force plate. The VICON infra-red camera system will capture the trial and after which, the data will be analysed by the study team member.

II. Questionnaire (Annex I and II)

This consists of 2 sets of self-administer questionnaire for parent and child respectively. The child's questionnaire on demographics, patient's perception on own health, mobility, emotions, activity (EQ-5D, ICF see below) and pain. The parent's questionnaire consist items on demographics, parent's perception on child's health, mobility, emotions, activity and resource use.

III. EuroQoL (EQ-5D)

EQ-5D is a standardised measure of health status in order to provide a simple, generic measure of health for clinical and economic appraisal.^{xiv} The EQ-5D-Y is the child-friendly

version. EQ-5D consists of the descriptive system and the EQ visual analogue scale (EQ VAS). The descriptive system comprises 5 dimensions. The EQ VAS records the respondent's self-rated health on a vertical, visual analogue scale where the endpoints are labelled 'The best health you can imagine' and 'The worst health you can imagine'. Parent or caregiver will be answering EQ-5D based on what they think the child feels. Whenever possible, for a child who can communicate and self-report assessment, EQ5D-Y will be used.

IV. ICF-CY

The WHO International Classification of Functioning, Disability and Health, Children & Youth version (ICF-CY) is a measure to grade function of activities of daily living (ADLs).^{xv} Few ICF-CY categories have been selected and graded based on the frequency, intrusiveness or severity of the specific impairment. (refer Table below).^{xvi}

The ICF-CY categories assessed and grading for each patient before and after intervention

ICF-CY categories	Illustration of grading
D420 Transferring oneself	0 = No impairment/ difficulty
D4153 Maintaining a sitting position	1 = mild impairment/ difficulty
B1340 Amount of sleep	(present <25% of time, intensity is tolerable, rare)
B1342 Maintenance of sleep	2 = moderate impairment/ difficulty
B1261 Agreeableness	(present <50% of time, intensity is interfering in day-to-day life, occasional)
B7356 Tone of all muscles of the body	3 = severe impairment/ difficulty
B7650 Involuntary contractions of muscle	(present >50% of time, intensity partially disruptive, often)
B2800 Generalised pain	4 = complete impairment/ difficulty (present >95% of time, intensity totally disruptive, constant)
	8 = not specified (insufficient information)
	9 = not applicable

V. Gross Motor Function measure (GMFM) (ANNEX VIII)

The Gross Moor Function Measure (GMFM) is an assessment tool designed and evaluated to measure changes in gross motor function over time or with intervention in children with cerebral palsy^{xvii}.

VI. Functional Assessment Questionnaire (FAQ) (ANNEX VIII)

The Functional Assessment Questionnaire (FAQ) is a 10 point scale (6–10 describe functional walkers with 10 being most able) which was designed specifically to be used as an outcome measure in individuals with physical disability.^{xviii}

VII. 10 Metre Walk Test (ANNEX VIII)

The 10 Metre Walk Test is a performance measure used to assess walking speed in metres per second over a short distance. It can be employed to determine functional mobility and gait.^{xix}

VIII. Goal Attainment Scale (GAS) (ANNEX VIII)

GAS is an individualised outcome measure involving goal selection and goal scaling that is

standardised in order to calculate the extent to which a patient's goals are met.^{xx}

Fitting

Child will be fitted with the Mollii suit and settings will be programmed by the Mollii suit company, Inverventions. The suit will be administered by trained physiotherapists from KKH. Child brings the Mollii suit home.

Intervention

Throughout the intervention period of 4 weeks, child will be wearing the Mollii suit for 60 min/ day every day. Parent will be keeping logs of compliance use, activity and adverse effect daily during this period. Child will be using the log book to document pain during this period. (Annex III)

Post-intervention

Immediately after intervention, child will undergo instrumented 3- dimensional gait analysis and objective assessments. Child and parent complete a questionnaire (Annex IV and VI) on health outcome measures and feasibility/ acceptability outcomes (refer Table 1).

1 months after intervention period, child will undergo objective assessments. Child and parent complete a questionnaire (Annex V and VII) on health outcome measures and feasibility/ acceptability outcomes (refer Table 1).

Table 2: SUMMARY OF STUDY VISITS

VIST 1:	Pre-intervention assessments: 
- Instrumented 3-dimensional gait study- Questionnaires (include EQ-5D, ICF)- GMFM- FAQ- 10m walk test- GAS	Patient will be charged for one PT session per standard care. Gait study is FOC
VISIT 2:	Collection of Mollii suit, settings for Mollii suit Signing of loan agreement	
@HOME 4WEEKS	Patient will wear Molli suit at home daily 1 hour for 4 weeks. Patient/ parent keep log logs of compliance use, pain and adverse effects.	
VISIT 3	Return Mollii Suit Post-intervention assessments: 
- Instrumented 3-dimensional gait study- Questionnaires (include EQ-5D, ICF)- GMFM	Patient will be charged for one PT session per standard care. Gait study is FOC

	
 - FAQ - 10m walk test - GAS 	
VISIT 4 (1 MTH LATER)	1month post-intervention assessments: 
 - Questionnaires (include EQ-5D, ICF) - GMFM - FAQ - 10m walk test 	Patient will be charged for one PT session per standard care.

4.3.3 Final Study Visit:

As per section 4.3.2

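### The 1-month stable-medication window is counted back from the intervention, yet the baseline gait score may be taken up to 2 weeks earlier: a minor, cheaply closed gap in an uncontrolled comparison

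*Protocol*

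**What the plan says.** Protocol 3.4 (Exclusion Criteria) excludes "Individuals who have had change in oral medication for spasticity 1 month prior intervention". The toxin and surgery criterion has the same anchor: "Individuals who have had Botulinum toxin done 6 months prior intervention or soft tissue release surgery done 6 months prior intervention". Both count back from the intervention.

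Protocol 4.3.2 sets the baseline assessments, including the instrumented gait analysis, at a different time, before the intervention starts: "within 2 weeks prior to fitting of Mollii suit". Table 2 confirms the separation: the gait study is at Visit 1 and suit collection and setting at Visit 2.

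The comparison rests on that first measurement. Section 1.2.4 states "This is a single-centre study that compares subjects before and after the intervention" and that "comparison is made in gait in the same individual". Section 2.2 names change in Gait Profile Score as the primary outcome, and section 4.1 rules out randomisation and blinding. No section applies the exclusion windows to the date of Visit 1.

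**The concern.** Section 3.4 gives no reason for its windows, but in a before-after study a period of stable treatment is useful mainly if it precedes the first measurement. Here it precedes fitting, a date on which no gait is measured. A child whose oral medication changed just over 1 month before fitting is eligible, yet may have been measured about 2 weeks after the change.

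If gait is still responding to the change at Visit 1, the remaining response falls between the two gait analyses and counts as pre-post change. A concurrent control group would share such drift on average; this design has none. At stake is a small bias in the primary estimate that could be avoided at almost no cost.

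**Working it through.** **Inputs from the protocol**
- Oral-medication window: 1 month, taken as 28 to 31 days (3.4).
- Toxin and surgery window: 6 months, taken as about 182 days (3.4).
- Baseline: 0 to 14 days before fitting (4.3.2). I treat fitting as the start of the intervention.
- Intervention: 4 weeks, with the second gait analysis immediately afterwards (4.3.2, Tables 1 and 2).
- Up to 20 children (3.1); difference 1.6, SD of the difference 2.4, two-sided 0.05, 80% power (9.1).

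**Step 1. The plan's own figure.** Standardised difference = 1.6 / 2.4 = 0.667. With the noncentral t distribution, power is 78.5% at n = 19 and 80.7% at n = 20, so 20 is the smallest sufficient number. It agrees with the enrolment figure in 3.1, and the present point does not alter it.

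**Step 2. Shortest gap from a treatment change to the baseline score**

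| Criterion | Window (days) | Less 14 days | Share lost |
|---|---|---|---|
| Oral medication | 28 | 14 | 14/28 = 50% |
| Oral medication | 31 | 17 | 14/31 = 45% |
| Toxin or surgery | about 182 | about 168 | 14/182 = 8% |

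The second gait analysis can follow baseline by up to 2 + 4 = 6 weeks.

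**Step 3. How many children could be affected.** The gap admits only children whose medication changed more than 1 month before fitting but less than 1 month before baseline. That band is as long as the interval from baseline to fitting, so at most 14 days. The documents give no rate of medication changes. For a rate of r changes per child-year, with every baseline at the 14-day limit:

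expected number = 20 × (14/365) × r = 0.77 × r

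- One affected child needs r = 1/0.77, about 1.3.
- Four affected children need r = 4/0.77, about 5.2.
- If baselines are spread evenly over 0 to 14 days (an assumption), the mean band is 7 days and these rates double to about 2.6 and 10.4.

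About 1 child of 20 is therefore a reasonable ceiling, and four is not realistic.

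**Step 4. Effect on the primary estimate.** Shift in mean change = (affected children / 20) × drift per child. The drift is not in the documents; I assume 0.8 to 1.6 points, that is, half to all of the target difference.

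- 1 child, 0.8 points: 0.8/20 = 0.04, or 2.5% of 1.6.
- 1 child, 1.6 points: 1.6/20 = 0.08, or 5% of 1.6.

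The standard error of the mean change is 2.4/√20 = 0.54, so the shift is about 7% to 15% of one standard error. If the suit has no effect and the drift is in its favour, the chance of a significant result favouring it rises from 2.5% to 2.9% (0.8 points) or 3.45% (1.6 points), by the noncentral t with 19 degrees of freedom.

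**The case against.** The best case for leaving the text alone is that the gap is narrow and its consequence small. This stands: few children can fall in the band, and the assumed drift is generous, since it credits a medication change already 2 weeks old with up to the full target difference. It also stands that 3.4 gives no rationale, so the purpose of the window is inferred, and that staff who apply the criteria at clinic screening (4.3.1) may in practice judge from an earlier date. That narrows the gap without closing it, because 4.3.1 refers them to 3.4 as written.

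The present anchor also does useful work: it excludes medication changes made between baseline and fitting. Moving it outright to Visit 1 would lose that protection.

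A reader might infer more than the documents support:
- *That the suit would be credited.* The sign is not fixed. A response still building at Visit 1 favours the suit; one wearing off, or following a reduction, could count against it.
- *That the bias could reach a fifth of the target difference.* That takes 4 of 20 children each drifting 1.6 points (4 × 1.6/20 = 0.32), which Step 3 shows to be unrealistic.
- *That the toxin and surgery windows are compromised alike.* They lose only about 8%.

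That 2 weeks is short does not answer the oral-medication criterion, where it is about half the window.

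**Conclusion.** The mismatch is real and rests on the text alone: 3.4 counts from the intervention, 4.3.2 puts the first primary measurement up to 14 days before it, and nothing connects the two. For oral medication, the guaranteed stable period before the baseline score can be as short as 14 to 17 days instead of 1 month.

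Its likely size is small. With at most about 1 of 20 children affected and an assumed drift of 0.8 to 1.6 points, the mean change moves by 0.04 to 0.08, in a direction that cannot be predicted. Both the number and the drift are assumptions. The point does not threaten the trial's conclusion or its sample size. It is a minor improvement worth making because it costs so little.

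**What to change.** Reconcile 3.4 with 4.3.2. Keep the stated 1-month length, and word the oral-medication exclusion to cover any change from 1 month before the baseline gait analysis (Visit 1) through fitting (Visit 2). Confirm this at Visit 2. Changes between baseline and fitting then stay excluded, as they are now. The toxin and surgery criterion may take the same anchor for consistency, with its length unchanged, though little is gained there.

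The cost is one amended sentence and one question at an existing visit, with no added measurement. A few children may have baseline delayed by up to 2 weeks. If a child were lost rather than delayed and no other enrolled, power at n = 19 would be 78.5% instead of 80.7%.

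The change has limits. It lengthens the minimum gap to baseline from 14–17 days to 28–31 days, which reduces residual effects but does not abolish them. It also does not reach medication changes during the 4 weeks: section 6.6 lets standard care continue and states no rule on such changes.
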